## **7.2 Study Population**

### **7.2.1 Disposition of Subjects**

The following subject data will be presented:

[Analysis population: All subjects with informed consent, Analysis group: Overall]

- Number of subjects with informed consent, discontinued before surgery period, entered surgery period, discontinued before registration, registered, enrolled in the observational cohort, randomized (overall only); and
- Number and percentage of subjects discontinued before surgery period, by primary reason for study discontinuation.

[Analysis population: All subjects with surgery period, Analysis group: Overall]

- Number and percentage of subjects discontinued before registration, by primary reason for study discontinuation.

[Analysis population: All randomized subjects, Analysis group: Randomization Arm and Total]

- Number and percentage of subjects randomized in each analysis set except PFAS;
- Number and percentage of subjects completed and discontinued the treatment period, by primary reason for treatment period discontinuation;
- Number and percentage of subjects completed and discontinued the follow-up period, by primary reason for follow-up period discontinuation; and
- Number and percentage of subjects excluded from each analysis set except PFAS by reason for exclusion defined in [Section 5.1; 5.2; 5.3; 5.4 and 5.5].

[Analysis population: subjects enrolled in the observational cohort and randomized to placebo group, Analysis group: Prognostic Factor Analysis Arm and Total]

- Number and percentage of subjects in PFAS.

[Analysis population: subjects enrolled in the observational cohort, Analysis group: NC negative]

- Number and percentage of subjects completed and discontinued the follow-up period, by primary reason for follow-up period discontinuation.

### **7.2.2 Protocol Deviations**

Protocol deviations as defined in the study protocol (Section 8.3 Major Protocol Deviations) will be assessed for all registered subjects. The number and percentage of subjects meeting any criteria will be summarized for each criterion and overall, by randomization arm and NC negative group as well as by study site. Subjects deviating from a criterion more than once will be counted once for the corresponding criterion. Any subjects who have more than one protocol deviation will be counted once in the overall summary. A data listing will be provided by site and subject.

The protocol deviation criteria will be uniquely identified in the summary table and listing. The unique identifiers will be as follows:

- PD1 - Entered into the study even though they did not satisfy entry criteria,
- PD2 - Developed withdrawal criteria during the study and was not withdrawn,
- PD3 - Received wrong treatment or incorrect dose,
- PD4 - Received excluded concomitant treatment.

### **7.2.3 Demographic and Other Baseline Characteristics**

[Analysis population: SAF, FAS, PPS, PKAS and PDAS, Analysis group: Randomization Arm and Total]

[Analysis population: PFAS, Analysis group: Prognostic Factor Analysis Arm and Total]

- Demographic and other baseline characteristics will be summarized by descriptive statistics and frequency tabulations [[Table 6](#)].
- Surgery parameters will be summarized by descriptive statistics and frequency tabulations [[Table 7](#)].
- AKI Risk Factors will be summarized by descriptive statistics and frequency tabulations [[Table 8](#)].

**Table 6 Demographic and Baseline Characteristics**

Item	Classification
Sex	1: Male 2: Female
Age (years) [Informed Consent]	Measurement value 1: < 65 2: >= 65
	1: < 70 2: >= 70
Ethnicity	1: Not Hispanic or Latino 2: Hispanic or Latino
Race	1: White 2: Black or African American 3: Asian 4: American Indian or Alaska Native 5: Native Hawaiian or Other Pacific Islander 6: Other
Height (cm) [Screening]	Measurement value
Weight (kg) [Screening]	Measurement value 1: < 60 2: >= 60
Tobacco History	0: Never 1: Current 2: Former
Alcohol History	0: Never 1: Current 2: Former
Drug Abuse	0: Never 1: Current 2: Former
Left Ventricular Ejection Fraction (%)	Measurement value 1: < 40 2: >= 40
AKIRisk Score ((ng/mL)  /1000) [Postsurgery] 	Measurement value 1: <= 0.3 2: > 0.3 to <= 0.7 3: > 0.7
eGFR for Randomization (mL/min/1.73 m  )	Measurement value 1: < 45 2: >= 45 1: < 60 2: >= 60
Peripheral Arterial Disease 	0: No 1: Yes
Use of Intravenous Radio-contrast 	0: No 1: Yes
Protocol Version Number at Enrollment	1: Before Version 2.0 2: Version 2.0 or Later

AKI: acute kidney injury; eGFR: estimated glomerular filtration rate

1: If AKIRisk Score at post surgery is recorded several times in eCRF, the last score will be used.

2: The record of “Are there any peripheral arterial diseases?” in Demographics eCRF will be used.

3: If subjects have at least one record in the Concomitant Medication eCRF with the flag selected “YES” for of use of Intravenous Radio-contrast between the date of screening and T0 of the date of surgery, then “Yes”; otherwise “No”.

**Table 7      Surgery parameters**

Item	Classification
Procedure of Surgery: CABG	0: No 1: Yes
Procedure of Surgery: Valve Surgery [Aortic]	0: No 1: Yes
Procedure of Surgery: Valve Surgery [Mitral]	0: No 1: Yes
Procedure of Surgery: Valve Surgery [Tricuspid]	0: No 1: Yes
Procedure of Surgery: CABG + Valve Surgery [Any]	0: No 1: Yes
Procedure of Surgery: Thoracic Aortic Surgery	0: No 1: Yes
Procedure of Surgery: ECMO	0: No 1: Yes
Procedure of Surgery: Use of VAD	0: No 1: Yes
Surgery Type 	1: Lower Risk Surgery 2: Higher Risk Surgery
Duration of CPB (hours)	Measurement value 1: < Median 2: >= Median
Duration of Aortic Cross-Clamp (hours)	Measurement value 1: < 0.5 2: >= 0.5 to < 1.0 3: >= 1.0
Lowest Intraoperative MAP (mmHg)	Measurement value
Duration from Incision to Closing of Skin (hours)	Measurement value
Urine Output During Surgery (mL/kg/h)	Measurement value
Total Fluid Intake During Surgery (mL)	Measurement value
Volume of Blood Products During Surgery (mL)	Measurement value
Use of Furosemide During Surgery	0: No 1: Yes
Dose of Furosemide During Surgery (mg)	Measurement value
Drain Output During Surgery (mL)	Measurement value
Volume of Blood Loss During Surgery (mL)	Measurement value
Redoing Surgery	0: No 1: Yes

CABG: coronary artery bypass graft; ECMO: Extracorporeal Membrane Oxygenation; VAD: ventricular assist device; CPB: cardiopulmonary bypass pump; MAP: mean arterial pressure

1: If the procedure of surgery is only one of CABG, Valve Surgery [Aortic], Valve Surgery [Mitral] or Valve Surgery [Tricuspid] and not Thoracic Aortic Surgery then Surgery type is “Lower Risk Surgery”; otherwise “Higher Risk Surgery”.

**Table 8 AKI Risk Factors**

Item	Classification
Circulatory Shock	0: No 1: Yes
Cardiovascular Surgery (Especially With CPB)	0: No 1: Yes
Nephrotoxic Drugs	0: No 1: Yes
Radiocontrast Agents	0: No 1: Yes
Poisonous Plants and Animals	0: No 1: Yes
Dehydration or Volume Depletion	0: No 1: Yes
Advanced Age ( $\geq 70$ years)	0: No 1: Yes
Female Gender	0: No 1: Yes
Black Race	0: No 1: Yes
CKD	0: No 1: Yes
Chronic Diseases (Heart, Lung, Liver)	0: No 1: Yes
Diabetes Mellitus	0: No 1: Yes
Anemia	0: No 1: Yes
Prior AKI	0: No 1: Yes

AKI: acute kidney injury; CPB: cardiopulmonary bypass pump; CKD: chronic kidney disease

[Analysis population: FAS and PPS, Analysis group: Randomization Arm and Total]

[Analysis population: PFAS, Analysis group: Prognostic Factor Analysis Arm and Total]

Baseline values of efficacy variables will be summarized by descriptive statistics and frequency tabulations [[Table 9](#)].

**Table 9 Baseline values of efficacy variables**

Item	Classification
Serum Creatinine (mg/dL)	Measurement value
Cystatin-C (mg/L)	Measurement value
eGFR based on Serum Creatinine (mL/min/1.73 m  )	Measurement value 1: < 45 2: >= 45 1: < 60 2: >= 60
eGFR based on Cystatin-C (mL/min/1.73 m  )	Measurement value 1: < 45 2: >= 45 1: < 60 2: >= 60

eGFR: estimated glomerular filtration rate

#### **7.2.4 Previous and Concomitant Medications**

All previous and concomitant medications will be presented in a listing.

#### **7.2.5 Duration of Study**

[Analysis population: SAF, Analysis group: Randomization Arm and Total]

[Analysis population: PFAS, Analysis group: Prognostic Factor Analysis Arm and Total]

The duration of study for each subjects will be summarized by descriptive statistics.

### **7.3 Study Drugs**

#### **7.3.1 Exposure and Treatment Compliance**

[Analysis population: SAF, Analysis group: Randomization Arm and Total]

The number of doses (1 time, 2 times or 3 times) and time of first study drug taken (within T0 + 8 hours, or after T0 + 8 hours) will be summarized in the frequency table. The time of first study drug taken will be summarized by protocol version number at enrollment (Before Version 2.0, Version 2.0 or Later).

### **7.4 Analysis of Efficacy**

#### **7.4.1 Analysis of Primary Endpoint**

##### **7.4.1.1 Primary Analysis**

[Analysis population: FAS, Analysis group: Randomization Arm]

- The primary efficacy endpoint of AKI (AKI-SCr72h) proportion will be analyzed using the Cochran-Mantel-Haenszel (CMH) test with strata to control for baseline eGFR based

on Serum Creatinine ( $< 45 \text{ mL/min per } 1.73 \text{ m}^2$ ,  $\geq 45 \text{ mL/min per } 1.73 \text{ m}^2$ ) on the FAS.

The hypothesis testing on the primary analysis will be performed at 2-sided 0.10 significance level to test the null hypothesis that the AKI-SCr72h proportion is equal between the 2 treatment arms vs the alternative hypothesis that AKI-SCr72h proportion is different between the ASP1128 arm vs the placebo arm.

- The Mantel-Haenszel (MH) estimate of the adjusted common risk ratio and 2-sided 90% confidence interval will be calculated.

If the proportion of subjects with baseline eGFR based on Serum Creatinine  $< 45 \text{ mL/min per } 1.73 \text{ m}^2$  for FAS is less than 10%, the above stratified analyses of CMH test and MH estimate of adjusted common risk ratio will be replaced with unstratified analyses of chi-square test and unadjusted risk ratio. It will also apply to the sensitivity analyses 2, 3 and 4 listed in [Table 10].

#### 7.4.1.2 Sensitivity Analysis

- As a sensitivity analysis for the primary endpoint of AKI (AKI-SCr72h) proportion, the chi-square test will be performed to evaluate the appropriateness of CMH test with strata to control for baseline eGFR based on Serum Creatinine ( $< 45 \text{ mL/min per } 1.73 \text{ m}^2$ ,  $\geq 45 \text{ mL/min per } 1.73 \text{ m}^2$ ). The estimate of the unadjusted risk ratio and 2-sided 90% confidence interval will be calculated. This analysis will be conducted using the FAS.
- Additional sensitivity analyses using other handlings of missing data will be performed to evaluate the impact on the analysis of AKI-SCr72h proportions due to any missing data/assessments and any loss to follow-up. If there is a missing value at any evaluation visit and the subject don't have the data meeting the criteria of the endpoint, then Multiple imputation (MI) will be conducted for each missing component data firstly, and AKI-SCr72h proportion will be derived based on the imputed data.
- In additional, different definition of handling of missing data will be used. The subjects whose status of AKI-SCr72h is unknown due to, say, the missing data of SCr will be counted as AKI-SCr72h event. That is, if there is a missing value at any evaluation visit, then the subject will be counted as AKI/MAKE event. The same analysis as primary analysis (CMH test) by using this handling of missing data will be performed.
- As a supplementary analysis, the same analysis of the primary endpoint as described in [Section 7.4.1.1 Primary Analysis] will be conducted using PPS.

[Table 10] summarizes all sensitivity analyses to be performed with the primary endpoint.

**Table 10 Primary and Sensitivity Analyses for Primary Endpoint**

Code	Set	Test	Handling of missing data
Primary	FAS	CMH test	Refer to 6.1
Sensitivity 1	FAS	Chi-square test	Same as Primary
Sensitivity 2	PPS	CMH test	Same as Primary
Sensitivity 3	FAS	CMH test	MI
Sensitivity 4	FAS	CMH test	Different Definition: missing data of SCr will be counted as AKI-SCr72h event

FAS: full analysis set; CMH: Cochran-Mantel-Haenszel; PPS: per protocol set; MI: multiple imputation; SCr: serum creatinine; AKI-SCr: acute kidney injury based on serum creatinine KDIGO criteria

### **CMH test with MI**

The MI CMH model will be used to compare ASP1128 and placebo group in a fixed sequence procedure:

1. Generate 1000 datasets, using seed 346194, where intermittent missing SCr value will be imputed for each treatment relying on non-missing data from all subjects within each treatment group using the Monte Carlo Markov Chain (MCMC) imputation model with treatment and the available non-missing SCr value for each scheduled Visit. The MCMC statement in the SAS PROC MI procedure with monotone option will be used. As a result, each dataset will only have missing ending data, or a monotone missing data pattern.
2. For each dataset from step 1, missing ending data (SCr value up through 72 hours after T0) will be imputed using seed 478034. As a result, 1000 imputed complete datasets will be generated.
  - Missing data at Visit 3 (T0 + 24 hours) will be imputed using the regression imputation model with the stratification factors, baseline and SCr value from Visit 3, using the SAS PROC MI procedure with the REGRESSION option in the MONOTONE statement.
  - The SAS PROC MI procedure will use data separately from each treatment subjects to impute the missing data for a specific Visit (i.e., only those that need the imputation for the Visit). Since subjects from the different treatment groups for that Visit are excluded from the step, they will not contribute to the imputation for the Visit.
  - Repeat for all other scheduled Visit sequentially (Visit 4 to 5). Subjects whose missing data were imputed for previous Visit will contribute to the imputation for the current Visit.

The regression imputation model includes an intercept and the slopes of the SCr value from previous Visit and the stratification factors.

3. The MH estimate of the adjusted common risk ratio, standard error and 2-sided 90% confidence interval for AKI-SCr72h proportion will be calculated using the observed or imputed SCr value.

4. Combine estimates from the results of each of the 1000 runs using SAS PROC MIANALYZE.

#### **7.4.2 Analysis of Secondary Endpoints**

[Analysis population: FAS, Analysis group: Randomization Arm]

- The secondary efficacy endpoints proportions (AKI-SCr7d, AKI-KDIGO72h, AKI-KDIGO7d, MAKE30 and MAKE90) will be analyzed using the stratified CMH test with strata to control for baseline eGFR based on Serum Creatinine (< 45 mL/min per 1.73 m^2, ≥ 45 mL/min per 1.73 m^2). The hypothesis testing will be performed at 2-sided 0.10 significance level. The MH estimate of the adjusted common risk ratio and 2-sided 90% confidence intervals will be calculated.
- As sensitivity analysis, chi-square test will be performed to evaluate the appropriateness of CMH test with strata to control for baseline eGFR based on Serum Creatinine (< 45 mL/min per 1.73 m^2, ≥ 45 mL/min per 1.73 m^2). The estimates of the risk ratio and 2-sided 90% confidence intervals will be calculated.
- Additional sensitivity analysis will be performed to evaluate the impact on the analysis of AKI/MAKE proportions due to any missing data/assessments and any loss to follow-up. If there is a missing value at any evaluation visit and the subject don't have the data meeting the criteria of the endpoint, then MI will be conducted for each missing component data firstly, then AKI/MAKE endpoint will be derived based on the imputed data.
- In additional, different definition of handling of missing data will be used. The subjects whose status of AKI/MAKE endpoint is unknown due to, say, the missing data of SCr will be counted as AKI/MAKE event. That is, if there is a missing value at any evaluation visit, then the subject will be counted as AKI/MAKE event. The same analysis as primary analysis (CMH test) by using this handling of missing data will be performed.
- As exploratory analyses, the association between MAKE30/MAKE90 (and also each individual outcomes, of all-cause mortality, initiation of RRT and eGFR based on SCr at day 30 (Visit 9)/day 90 (Visit 10) equal to or less than 75% of the baseline value) and primary, secondary and exploratory endpoint of AKI proportion is evaluated by a contingency table. The following endpoints of AKI proportion will be used:
  - AKI-SCr72h (primary endpoint),
  - AKI-SCr7d (secondary endpoint),
  - AKI-KDIGO72h (secondary endpoint),
  - AKI-KDIGO7d (secondary endpoint),
  - All stages AKI-UO (within 72 hours after T0)
  - All stages AKI-UO (within 7 days after T0),
  - AKI-UO stage 3 (within 72 hours after T0),
  - AKI-UO stage 3 (within 7 days after T0),

- AKI-SCr stage 2 or 3 (within 72 hours after T0),
- AKI-SCr stage 2 or 3 (within 7 days after T0),
- AKI-SCr stage 2 or 3 and/or AKI-UO stage 3 (within 72 hours after T0),
- AKI-SCr stage 2 or 3 and/or AKI-UO stage 3 (within 7 days after T0),
- AKI based on Cystatin-C, defined as an increase of  $\geq 10\%$  of baseline Cystatin-C (within 72 hours after T0),
- AKI based on Cystatin-C, defined as an increase of  $\geq 10\%$  of baseline Cystatin-C (within 7 days after T0),
- AKI-SCr5d,
- AKI-KDIGO5d,
- AKI as defined by a 50% or higher reduction in eGFR based on the Cystatin-C equation within 72 hours after T0, and
- AKI as defined by a 50% or higher reduction in eGFR based on the Cystatin-C equation within 7 days after T0.

If the proportion of subjects with baseline eGFR based on Serum Creatinine  $< 45$  mL/min per  $1.73\text{ m}^2$  for FAS is less than 10%, the above stratified analyses of CMH test and MH estimate of adjusted common risk ratio will be replaced with unstratified analyses of chi-square test and unadjusted risk ratio.

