Study drug will need to be prepared for infusion by the study staff in the ICU. A detailed instruction is described in the pharmacy manual. The pH of the solution for injection is around 10 and there is a minor risk for irritation at the infusion site. Based on the results of the phase 1 study in healthy subjects it was determined that administration via a central line is allowed, but not required. The study drug can also be infused in a peripheral line on the forearm. The chosen peripheral line has to be reserved for study drug administration to avoid physicochemical interaction. If subjects have a central line this can be used for administration of study drug provided that 1 of the lumina is reserved for study drug in order to avoid physicochemical interactions.

After surgery, UO will be monitored, safety assessments will be done and laboratory tests (including NC, serum creatinine (SCr; cystatin-C and other biomarkers) will be performed as per the Schedule of Assessments [[Table 1](#)].

#### Visit 3, 4 and 5

It is expected that the subject will leave the ICU within 12 to 48 hours after surgery, but will remain in the hospital. Drug administration may be done via a central line in the ICU; however, this central line may have to be removed when the subject leaves the ICU. In this case, the study drug can also be infused in a peripheral line on the forearm. The chosen peripheral line has to be reserved for study drug administration to avoid physicochemical interaction. Please note that blood samples for pharmacokinetic measurements should be taken from a different location than the location of the peripheral intravenous device used for drug administration. A detailed instruction on drug preparation and administration is described in the pharmacy manual.

If the first dose of IP administration is completed within 8 hours after T0, the second dose of IP will be administered at 24 hours after T0 and the third dose of IP will be administered at 48 hours after T0. If the first dose of IP administration is completed past 8 hours after T0, the second dose of IP will be administered at 16 hours after the start of the first dose, and the third dose of IP will be administered at 40 hours after the start of the first dose of IP.

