#### 5.3.1.2 Urinary Output

For randomized subjects, UO every 12 hours and total fluid intake every 24 hours will be recorded when the subject is in the ICU. During the first 72 hours following surgery (i.e., visit 3 to visit 5) the investigator will record information on AKI-UO stages 1 to 3 in the eCRF to assess their occurrence as per investigator discretion. When the subject is discharged from the ICU, but is still in the hospital, UO and fluid intake every 24 hours will be recorded up to day 7 (visit 8).

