## **4 SAMPLE SIZE**

Sample size of this study is 220 randomized subjects (110 subjects in the ASP1128 group and 110 subjects in the placebo group).

The above sample size provides 80% power to detect the difference between ASP1128 and placebo on the primary endpoint of AKI proportion in the case of not considering an interim analysis, assuming the followings:

- AKI proportion in the placebo group is 60%
- Relative risk of ASP1128 against placebo is 0.7 (30% reduction)
- 1-sided significance level is 0.05
- Drop-out rate is around 10%

In addition, an interim analysis at 60% of enrollment as described below is planned by East® 6 software. Considering the interim analysis, the power is 78%.

- Futility stop criteria: conditional power to detect the relative difference between ASP1128 and placebo on the primary endpoint of AKI proportion is less than 10%, that is, 1-sided p-value is larger than 0.259, when approximately 60% of the planned acute kidney injury based on serum creatinine within 72 hours after Time point 0 (T0) (AKI-SCr72h) data have been collected in the study.
- There will be no provision to stop the study for efficacy in the interim analysis, so no efficacy stop criteria are defined.

Approximately 1000 subjects will be screened to enroll 600 subjects who meet the presurgery selection criteria. It is expected that 1 out of 3 subjects enrolled will meet the postsurgery criterion of having a NC AKIRisk score  $> 0.3 \text{ (ng/mL)}^2/1000$  and can be randomized: the

number of subjects to be randomized is 220. The subjects that have an AKIRisk score of  $\leq 0.3$  at the postsurgery 2- to 6-hour assessment will be enrolled in the observational cohort.

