### 6.1.2 Secondary Efficacy Endpoints

1. Proportion of subjects developing AKI (any stage) based on SCr criteria from the KDIGO guideline within 7 days after T0 (i.e., until Visit 8) (AKI-SCr7d).

[SCr evaluation visit: baseline, Visit 3, 4, 5, 6, 7 and 8 (24 hours, 48 hours, 72 hours after T0, and Day 5, 6 and 7/DoD). If the hospital discharge is earlier than Day 7, then the visits prior to DoD and Visit 8 (DoD) will be used.]

- If the subject meets at least one of the following conditions, then the subject will be treated as developing AKI-SCr7d.
  - Increasing in SCr  $\geq 0.3 \text{ mg/dL}$  within any 48 hours until Visit 8; and/or,
  - Increasing in SCr  $\geq 1.5$  times baseline until Visit 8.

2. Proportion of subjects developing AKI based on all captured criteria from the KDIGO guideline within 72 hours after T0 (AKI-KDIGO72h).

[SCr evaluation visit: baseline, Visit 3, 4 and 5 (24, 48, 72 hours after T0)]

[UO evaluation visit: Visit 3, 4, and 5 (0-12 hours, 12-24 hours, 0-24 hours, ..., and 48-60 hours, 60-72 hours and 48-72 hours after T0)]

- If the subject meets at least one of the following conditions, then the subject will be treated as developing AKI-KDIGO72h.
  - Increasing in SCr  $\geq 0.3$  mg/dL within any 48 hours until Visit 5;
  - Increasing in SCr  $\geq 1.5$  times baseline until Visit 5; and/or,
  - Urine volume  $< 0.5$  ml/kg per hour for any one of 12 consecutive hours until Visit 5 (i.e., 0-12 hours after T0, 12-24 hours after T0, ..., or 60-72 hours after T0).
- 3. Proportion of subjects developing AKI based on all criteria from the KDIGO guideline within 7 days after T0 (AKI-KDIGO7d).

[SCr evaluation visit: baseline, Visit 3, 4, 5, 6, 7 and 8(24 hours, 48 hours, 72 hours after T0, and Day 5, 6 and 7/DoD). If the hospital discharge is earlier than Day 7, then the visits prior to DoD and Visit 8 (DoD) will be used.]

[UO evaluation visit: Visit 3, 4, 5, 6, 7 and 8 (0-12 hours, 12-24 hours, 0-24 hours, ..., and 120-132 hours, 132-144 hours and 120-144 hours after T0). If the hospital discharge is earlier than Day 7, then the visits prior to DoD and Visit 8 (DoD) will be used.]

  - If the subject meets at least one of the following conditions, then the subject will be treated as developing AKI-KDIGO7d.
    - Increasing in SCr  $\geq 0.3$  mg/dL within any 48 hours until Visit 8;
    - Increasing in SCr  $\geq 1.5$  times baseline until Visit 8; and/or,

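### Read literally, the missing-as-event sensitivity rule for AKI-KDIGO72h and AKI-KDIGO7d scores as AKI the 12-hour urine volumes that the protocol does not collect after ICU exit

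*SAP*

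**What the plan says.** **Endpoint.** SAP 6.1.2 (item 2) sets the urine assessments for AKI-KDIGO72h as "UO evaluation visit: Visit 3, 4, and 5 (0-12 hours, 12-24 hours, 0-24 hours", continuing in that pattern to 72 hours. The criterion is output below 0.5 mL/kg/h in any one of the 12-hour windows, the last being 60-72 hours. Item 3 does the same for AKI-KDIGO7d, with windows to 132-144 hours. The 24-hour windows are listed, but the criterion does not use them.

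**Collection.** Protocol 5.3.1.2 and footnote 8 of the Schedule of Assessments (Table 1) require 12-hourly volumes while the subject is in the ICU. Footnote 8 limits this to T0 through 72 hours; section 5.3.1.2 has no such limit. For the ward, as far as day 7, section 5.3.1.2 reads: "When the subject is discharged from the ICU, but is still in the hospital, UO and fluid intake every 24 hours will be recorded". Protocol 2.2.1 (Visit 3, 4 and 5) states: "It is expected that the subject will leave the ICU within 12 to 48 hours after surgery".

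**Missing-data rules.** SAP 7.4.2 adds two sensitivity analyses. One uses multiple imputation for subjects who have a missing value and do not already meet the endpoint. The other applies the rule that "if there is a missing value at any evaluation visit, then the subject will be counted as AKI/MAKE event". The only imputation model written out, in SAP 7.4.1.2, covers serum creatinine through 72 hours.

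**The concern.** The missing-as-event rule is meant to show what happens if every lost observation hides an event. Here most of the absent values are not lost: the protocol never asks for them once the subject is on the ward. A subject who follows the expected course, with normal creatinine and good urine output throughout, is still counted as AKI because the later 12-hour windows are empty. Both arms then move towards 100%, and the analysis reflects the recording schedule more than the drug. A risk ratio near 1 for two of the five secondary endpoints could be taken to mean that the result is not robust to missing data.

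**Working it through.** **1. The plan's own figure.** SAP section 4 gives the inputs: "Sample size of this study is 220 randomized subjects", 1:1; placebo AKI proportion 60%; relative risk 0.7, so ASP1128 is 0.7 × 60% = 42%; "1-sided significance level is 0.05"; drop-out about 10%, so 110 × 0.9 = 99 per arm. With p̄ = 0.51:

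power = Φ{[0.18 − 1.645 × √(2 × 0.51 × 0.49 / 99)] / √[(0.60 × 0.40 + 0.42 × 0.58) / 99]} = Φ{(0.180 − 0.117) / 0.0699} ≈ 0.82.

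This agrees with the stated 80%. These rates belong to AKI-SCr72h. The documents give none for the AKI-KDIGO endpoints, so they serve here as an illustration.

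**2. Windows missing by design.** Twelve-hour windows observed = ICU hours / 12.

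| ICU exit | Missing of 6 (72h endpoint) | Missing of 12 (7d endpoint, full 7-day stay) |
|---|---|---|
| 12 h | 5 | 11 |
| 24 h | 4 | 10 |
| 36 h | 3 | 9 |
| 48 h | 2 | 8 |
| 72 h | 0 | 6 |

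Across the expected range of 12 to 48 hours, no subject has all windows. If footnote 8 governs, the six windows from 72 to 144 hours have no scheduled 12-hour volume even in the ICU. Discharge before day 7 removes later visits from the 7d endpoint but not the ward windows before discharge.

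**3. Effect of the literal rule.** Let f be the share of subjects with every 12-hour window observed, assumed independent of arm and outcome. The scored proportion is (1 − f) + f × p. For f = 5%: placebo 0.95 + 0.05 × 0.60 = 98.0%; ASP1128 0.95 + 0.05 × 0.42 = 97.1%; ratio 0.991.

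| f (assumed) | Placebo | ASP1128 | Risk ratio | Power, 99 per arm |
|---|---|---|---|---|
| 0% | 100% | 100% | 1 | no test possible |
| 5% | 98.0% | 97.1% | 0.991 | 11% |
| 10% | 96.0% | 94.2% | 0.981 | 15% |
| 20% | 92.0% | 88.4% | 0.961 | 21% |
| 50% | 80.0% | 71.0% | 0.887 | 43% |
| 100% | 60.0% | 42.0% | 0.700 | 82% |

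Power uses the normal approximation of step 1, which is rough when proportions are close to 1.

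**4. Reach of the imputation.** Subjects already meeting the endpoint are not imputed. At design creatinine rates, at most 1 − 0.60 = 40% of placebo and 1 − 0.42 = 58% of ASP1128 subjects could be, or (40 + 58) / 2 = 49% overall. For these subjects SAP 7.4.2 asks that each missing component be imputed, but no urine-volume model is given.

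**5. What a 24-hour total can show.** If both 12-hour halves are at least 0.5 mL/kg/h, so is the 24-hour mean. A mean below 0.5 therefore proves a low half. The converse fails: halves of 0.3 and 0.9 average 0.6.

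**The case against.** The strongest reply is that the rule speaks of a missing value at an evaluation visit, for subjects whose status is unknown. The urine evaluation visits are Visits 3, 4 and 5, and SAP 6.1.2 lists 24-hour windows that match ward recording. On that reading a ward subject with a 24-hour total has a value, is not missing, and the collapse disappears (the last row of the table in step 3). This reading is possible, but the SAP does not state it, and the criterion itself uses only 12-hour windows. To 72 hours the eCRF also holds investigator-recorded AKI-UO stages; the SAP does not say whether they count. What stands of the reply is that the outcome depends on an unwritten choice, and the literal text gives the degenerate answer.

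Three stronger readings are tempting, and the documents do not support them:

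- A reader might infer that the risk ratio is certain to be 1 whatever the drug does. That needs every subject to leave the ICU before the last window. The protocol gives an expectation of 12 to 48 hours, not a distribution.
- A reader might infer that almost every subject would be imputed. Observed events are not imputed, so the ceiling is about half at design rates.
- A reader might infer that ward volumes would be imputed from the sicker subjects still in the ICU. No urine-volume model is written, so that mechanism cannot be attributed to the SAP. The documented fault is the missing model.

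**Conclusion.** The concern holds for the missing-as-event sensitivity analyses of AKI-KDIGO72h and AKI-KDIGO7d under the literal wording. On the protocol's own expectation of ICU stay, 2 to 5 of the 6 windows to 72 hours are absent by design, and both arms drift towards 100% events. The size depends on the share of subjects with complete windows, which the documents do not give. Over an assumed 5% to 50%, a risk ratio of 0.70 becomes 0.99 to 0.89, with f taken as independent of arm and outcome and the AKI-SCr72h design rates standing in for the AKI-KDIGO rates.

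The scope is limited. AKI-SCr72h uses no urine data, and SAP 7.4.2 presents the rule as a different definition from that of the main secondary analyses. The imputation analysis has a separate gap: it asks for imputation of components for which no model exists. Both are worth correcting, because a stated rule that degenerates when followed is more than missing detail.

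**What to change.** In SAP 7.4.2, for AKI-KDIGO72h and AKI-KDIGO7d:

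1. Apply missing-as-event only to creatinine visits and to urine records that the protocol schedules: 12-hour volumes while in the ICU, the 24-hour total on the ward. A 12-hour window not scheduled on the ward is not counted as missing.
2. Count a ward 24-hour mean below 0.5 mL/kg/h as meeting the urine criterion, since at least one 12-hour half must be below 0.5. State the limitation that a mean at or above 0.5 does not exclude a low half, so ward non-events are less certain than ICU non-events.
3. Restrict multiple imputation for these endpoints to creatinine, or specify a urine-volume imputation model.

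The cost is SAP wording and programming. No new data are needed.
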